### **18. Monitoring**

Monitoring will be performed during the study according to the monitoring plan to assess continued compliance with the protocol and applicable regulations. In addition, the monitor verifies that study records are adequately maintained, that data are reported in a satisfactory

manner with respect to timeliness, adequacy, and accuracy, and that the Investigator continues to have sufficient staff and facilities to conduct the study safely and effectively. The Investigator/institution guarantees direct access to original source documents by BSC personnel, their designees, and appropriate regulatory authorities.

The study may also be subject to a quality assurance audit by BSC or its designees, as well as inspection by appropriate regulatory authorities. It is important that the Investigator and relevant study personnel are available during on-site monitoring visits or audits and that sufficient time is devoted to the process.

## 19. Potential Risks and Benefits

Risks to clinical subjects associated with their participation in this clinical investigation, arising from the clinical procedures set out in the study protocol, have been identified from prior studies conducted by Boston Scientific Corporation and review of relevant literature, most recently from the Edwards Lifesciences' Placement of Aortic Transcatheter Valves (PARTNER) Trial, the PARTNER II trial, the SAPIEN 3 CE Mark study, the CoreValve Extreme Risk Study, the CoreValve High Risk Study, and the PORTICO IDE randomized trial/RESOLVE registry/SAVORY registry.

Benefits to subjects anticipated to arise from the use of the investigational device have also been identified. These clinical risks and benefits are summarized below, with an assessment of the balance of risks and benefits to subjects.

Potential risks and benefits have been included in the study-specific template of the ICF provided to the study centers (see Section 0).

### 19.1. *Risks Associated with Transcatheter Aortic Valve Implantation Procedure*

Adverse events (in alphabetical order) potentially associated with transcatheter aortic valve implantation (including standard cardiac catheterization, BAV, and the use of anesthesia) as well as additional risks related to the use of the Lotus Valve System/LOTUS Edge Valve System and/or CoreValve include but may not be limited to the following.

- Abnormal lab values (including anemia and electrolytes)
- Allergic reaction (including to medications, anesthesia, contrast, or device materials)
- Angina
- Arrhythmia or new conduction system injury (including need for pacemaker insertion)
- Bleeding or hemorrhage (possibly requiring transfusion or intervention)
- Cardiac arrest
- Cardiac failure/low cardiac output
- Cerebrovascular accident, stroke or transient ischemic attack
- Coronary obstruction

- Death
- Device misplacement or migration
- Endocarditis
- Emboli (including air, calcium, tissue, thrombus or device materials)
- Fever
- Heart failure
- Hemolysis and/or hemolytic anemia
- Hematoma or lymphatic problems at the access sites
- Hemodynamic instability or shock
- Hypertension/hypotension
- Infection (local and/or systemic, including septicemia)
- Inflammation
- Mitral valve insufficiency
- Myocardial infarction
- Myocardial or valvular injury (including perforation or rupture)
- Nerve injury
- Pain
- Pericardial effusion or cardiac tamponade
- Peripheral ischemia or infarction
- Permanent disability
- Pleural effusion
- Pulmonary edema
- Renal insufficiency or failure
- Respiratory insufficiency or failure
- Valve dysfunction, deterioration or failure
- Valvular stenosis or regurgitation (central or paravalvular)
- Valve or device thrombosis
- Vessel injury (including spasm, trauma, dissection, perforation, rupture, arteriovenous fistula, or pseudoaneurysm)

As a result of these complications, the subject may require medical, percutaneous or surgical intervention, including re-operation and replacement of the implanted valve. Such complications can be fatal.

As the Lotus Valve/LOTUS Edge Valve is an investigational device, uncertainty remains over risks of experiencing some or all of the complications listed above. There may be risks that are unknown at this time.

## 19.2. Risk Minimization Actions

Additional risks may exist. Risks can be minimized through compliance with this protocol, performing procedures in the appropriate hospital environment, adherence to subject selection criteria, close monitoring of the subject's physiologic status during research procedures and/or follow-ups and by promptly supplying BSC with all pertinent information required by this protocol.

- Boston Scientific Corporation will employ measures throughout the course of this investigation consistent with the best practices and lessons learned from other ongoing TAVR trials and commercial use to minimize risk for subjects choosing to participate. All efforts will be made to minimize risks by selecting centers that are experienced and skilled in TAVR procedures.
- Risk mitigation will be accomplished through the following actions.
  - Clearly defining the inclusion/exclusion criteria to ensure only appropriate subjects are enrolled
  - Confirmation of eligible subjects by a Case Review Committee, including experienced investigators in TAVR
  - Ensuring that treatment and follow-up of the subject are consistent with current medical practices
  - Selection of investigators who are experienced and skilled in TAVR procedures
  - Completion of training and proctorship provided by the Sponsor
  - Performing all procedures in accordance with the IFU, including the preparation of the valve and delivery system
  - Dynamic safety review processes, including assessment by the Data Monitoring Committee (DMC, Section 22.1) and CEC (Section 22.1) adjudication of specified events as recommended by VARC.

In addition to its repositioning and self-centering features designed to facilitate optimal positioning, the Lotus Valve System/LOTUS Edge Valve System provides physicians with control throughout the procedure by allowing them to pause, assess, lock, un-lock, incrementally reverse, resheath and, if needed, retrieve the valve prior to final release. These features help the physician to do the following: place the valve correctly with the first attempt, reposition the device if the initial deployment is considered to be suboptimal, and

retrieve the device if during the procedure the decision is made not to implant. The valve's outer seal is also designed to minimize paravalvular leakage.

Anticoagulation medication (e.g., heparin) will be administered during the procedure to reduce the risk of embolism and stroke. Additionally, post-procedure anti-platelet therapy is recommended to minimize any risk of thrombus formation, stroke, or transient ischemic attack. Neurological assessments will be performed at each required follow-up visit to identify any change in the neurological status of the subjects as recommended by VARC.

Cardiac enzyme measurements as well as ECGs post-procedure will be performed to detect periprocedural MI.

Subjects will be carefully monitored during the procedure, hospitalization, and throughout the follow-up period. Serial echocardiograms and electrocardiograms will be used to evaluate valve and general cardiac function. Any abnormal rhythm will be assessed and, if needed, the implantation of a permanent pacemaker will be performed. Annual imaging will also be performed to assess for structural valve frame integrity.

Subjects who are converted to standard surgical aortic valve replacement will be carefully monitored in a method appropriate for their surgical procedure.

Data will be monitored as they are submitted to BSC. Qualified employees of BSC, or a designee under contract, will conduct monitoring visits at the initiation of the study and at interim intervals described in the monitoring plan throughout the course of the study to evaluate protocol compliance and determine if there are any issues that could affect the safety or welfare of any subject in the study.

### **19.3. *Anticipated Benefits***

#### **19.3.1. Potential Benefits to the TAVR Procedure**

Transcatheter aortic valve replacement (TAVR) may offer certain advantages when compared to surgical replacement of the stenotic native aortic valve, particularly in high risk subjects. Known benefits associated with TAVR, as described in the scientific literature (see summary in Section 4.1 of this document and details in Sections 2 and 3 of the investigator brochure), potentially include the following.

- Minimally invasive procedure and reduced risks related to open heart surgery
- Shorter stay in the intensive care unit and overall hospital stay
- Reduced blood loss
- More rapid recovery
- Reduced need for general anesthesia and associated risks
- Opportunity to receive a new aortic prosthesis in spite of having been refused surgery or being of high surgical risk profile

### 19.3.2. Potential Benefit Using the Lotus Valve System/LOTUS Edge Valve System

Potential benefits that may be associated specifically with use of the Lotus™ Valve System/LOTUS Edge™ Valve System compared to other TAVR systems include the following.

- Pre-loaded delivery system minimizing time required and potential issues with preparing the device
- Accurate valve placement due to the ability to reposition the valve during deployment
- Device is minimally obstructive to the blood flow and maintains hemodynamic stability through the annulus during delivery because there is no balloon or other obstructive device required for deployment and due to early valve leaflet function
- Reduced need for post-dilation
- Reduced or obviated need for valve-in-valve repeat intervention
- Lower risk of ectopic valve placement and valve migration
- Reduced incidence of paravalvular aortic regurgitation due to the Adaptive Seal

### 19.4. Risk to Benefit Rationale

Review of the aforementioned clinical benefits versus risks takes into account the known risks/benefits that have been identified in the published literature on other TAVR devices. The estimation of risk also includes prior limited clinical experience with the Lotus Valve System including earlier generations of the device design. When used according to the IFU, all known risks associated with the TAVR procedure and the specific use of the Lotus Valve System are mitigated to acceptable limits comparable to existing TAVR devices. The design features of full repositioning and retrievability may improve TAVR procedural safety. The Adaptive Seal may provide long term benefit as it is designed to minimize paravalvular regurgitation, which has been associated with long term mortality in TAVR. No new hazards/harms are introduced by the LOTUS Edge Valve System compared to the Lotus Valve System when used with the Lotus Introducer Set. Because the overall risk profile of the device has not changed, it can be concluded that the potential benefits of the use of the LOTUS Edge Valve System with the Lotus Introducer Set out-weigh the risks.

## 20. Informed Consent

Subject participation in this clinical study is voluntary. Informed Consent is required from all subjects or their legally authorized representative. The Investigator is responsible for ensuring that Informed Consent is obtained prior to the use of any investigational devices, study-required procedures and/or testing, or data collection.

The obtaining and documentation of Informed Consent must be in accordance with the principles of the Declaration of Helsinki; the relevant parts of ISO 14155: 2011 and the ICH

guidelines for GCP; any applicable national regulations; and local Ethics Committee and/or Regulatory authority body, as applicable. The ICF must be approved by the center's IRB/EC, or central IRB, if applicable.

Boston Scientific Corporation will provide a study-specific template of the ICF to investigators participating in this study. The ICF template may be modified to meet the requirements of the investigative center's IRB/EC. Any modification requires approval from BSC or authorized representative prior to use of the form. The ICF must be in a language understandable to the subject and if needed, BSC will assist the center in obtaining a written consent translation. Translated consent forms must also have IRB/EC approval prior to their use. Privacy language shall be included in the body of the form or as a separate form as applicable.

The process of obtaining Informed Consent shall:

- be conducted by the Principal Investigator or designee authorized to conduct the process,
- include a description of all aspects of the clinical study that are relevant to the subject's decision to participate throughout the clinical study,
- avoid any coercion of or undue influence of subjects to participate,
- not waive or appear to waive subject's legal rights,
- use native language that is non-technical and understandable to the subject or his/her legal representative,
- provide ample time for the subject to consider participation and ask questions if necessary,
- ensure important new information is provided to new and existing subjects throughout the clinical study.

The ICF shall always be signed and personally dated by the subject or legal representative and by the investigator or an authorized designee responsible for conducting the informed consent process. If a legal representative signs, the subject shall be asked to provide informed consent for continued participation as soon as his/her medical condition allows. The original signed ICF will be retained by the center and a copy of the signed and dated document and any other written information must be given to the person signing the form.

Failure to obtain subject consent will be reported by BSC to the applicable regulatory body according to their requirements. Any violations of the informed consent process must be reported as deviations to the Sponsor and local regulatory authorities (e.g. IRB/EC), as appropriate.

If new information becomes available that can significantly affect a subject's future health and medical care, that information shall be provided to the affected subject(s) in written form via a revised ICF or, in some situations, enrolled subjects may be requested to sign and date an addendum to the ICF. In addition to new significant information during the course of a study, other situations may necessitate revision of the ICF, such as if there are amendments to the protocol, a change in Principal Investigator, administrative changes, or following

annual review by the IRB/EC. The new version of the ICF must be approved by the IRB/EC. Boston Scientific Corporation approval is required if changes to the revised ICF are requested by the center’s IRB/EC. The IRB/EC will determine the subject population to be re-consented.

## 21. Safety Reporting

### 21.1. Definitions and Classification

Adverse event definitions are provided in Table 21.1-1.

**Table 21.1-1: Adverse Event Definitions**

Term	Definition a
Adverse Event (AE) Ref: ISO 14155:2011	Any untoward medical occurrence, unintended disease or injury or untoward clinical signs (including abnormal laboratory findings) in subjects, users or other persons, whether or not related to the investigational medical device  Note 1: This definition includes events related to the investigational medical device or the comparator. Note 2: This definition includes events related to the procedures involved. Note 3: For users or other persons, this definition is restricted to events related to investigational medical devices.
Adverse Device Effect (ADE) Ref: ISO 14155:2011	Adverse event related to the use of an investigational medical device Note 1: This definition includes adverse events resulting from insufficient or inadequate instructions for use, deployment, implantation, installation, or operation, or any malfunction of the investigational medical device. Note 2: This definition includes any event resulting from use error or from intentional misuse of the investigational medical device.
Serious Adverse Event (SAE) Ref: ISO 14155:2011	Adverse event that: 
 
• Led to a death
 
• Led to serious deterioration in the health of the subject, that either resulted in:                             
 
○ a life-threatening illness or injury, or
 
○ a permanent impairment of a body structure or a body function, or
 
○ in-patient or prolonged hospitalization, or
 
○ medical or surgical intervention to prevent life- threatening illness or injury or permanent impairment to a body structure or a body function,
 
 
 
• Led to fetal distress, fetal death or a congenital abnormality or birth defect
 
 Note: Planned hospitalization for a pre-existing condition, or a procedure required by the protocol, without serious deterioration in health, is not considered a serious adverse event.
Serious Adverse Device Effect (SADE) Ref: ISO 14155:2011	Adverse device effect that has resulted in any of the consequences characteristic of a serious adverse event.

**Table 21.1-1: Adverse Event Definitions**

Term	Definition a
Unanticipated Adverse Device Effect (UADE)  Ref: 21 CFR Part 812	Any serious adverse effect on health or safety or any life-threatening problem or death caused by, or associated with, a device, if that effect, problem, or death was not previously identified in nature, severity, or degree of incidence in the investigational plan or application (including a supplementary plan or application), or any other unanticipated serious problem associated with a device that relates to the rights, safety, or welfare of subjects.
Unanticipated Serious Adverse Device Effect (USADE)  Ref: ISO 14155:2011	Serious adverse device effect which by its nature, incidence, severity or outcome has not been identified in the current version of the risk analysis report Note: Anticipated serious adverse device effect (ASADE) is an effect which by its nature, incidence, severity or outcome has been identified in the risk analysis report.
Device Deficiency  Ref: ISO 14155:2011 Ref: MEDDEV 2.7/3 12/2010	A device deficiency is Any inadequacy of a medical device with respect to its identity, quality, durability, reliability, safety or performance. Note 1: Device deficiencies include malfunctions, use errors, and inadequate labeling.  Note 2: All device deficiencies that could have led to a SADE if a) suitable action had not been taken or b) if intervention had not been made or c) if circumstances had been less fortunate shall be reported as required by the local IRB/EC, national regulations, or the protocol.

a: Other definitions may apply per local reporting requirements.

Underlying diseases are not reported as AEs unless there is an increase in severity or frequency during the course of the investigation. Death should not be recorded as an AE, but should only be reflected as an outcome of a specific SAE (see Table 21.1-1 for AE definitions).

In-patient hospitalization is defined as the subject being admitted to the hospital, with the following exceptions.

- A hospitalization that is uncomplicated and elective/planned (i.e., planned prior to enrollment) does not have to be reported as an SAE.
- If complications or AEs occur during an elective/planned (i.e., planned prior to enrollment) hospitalization after enrollment, the complications and AEs must be reported as AEs or SAEs if they meet the protocol-specified definitions.

For the randomized cohort, event reporting (eCRF) is required beginning from the time of randomization.

For the roll-in, Lotus 21 mm Nested Registry, LOTUS Edge Nested Registry, roll-in with the 29 mm LOTUS Edge, LOTUS Edge 29 mm Nested Registry, and U.S. Continued Access Study cohorts, event reporting (eCRF) is required beginning from the time an attempt is made to insert the Lotus Valve System/LOTUS Edge Valve System into the subject's femoral artery.

Refer to Section 19 for the known risks associated with the study devices (test and control). Based on the VARC recommendations and definitions, the adverse events and/or safety endpoints requiring adjudication by the CEC include the following.

- Mortality: all-cause, cardiovascular, and non-cardiovascular
- Stroke: disabling and non-disabling
- Myocardial infarction (MI): periprocedural ( $\leq 72$  hours post index procedure) and spontaneous ( $> 72$  hours post index procedure)
- Bleeding events: life-threatening (or disabling) and major
- Acute kidney injury ( $\leq 7$  days post index procedure): based on the AKIN System Stage 3 (including renal replacement therapy) or Stage 2
- Vascular complications: major
- Repeat procedure for valve-related dysfunction (surgical or interventional therapy)
- Hospitalization for valve-related symptoms or worsening congestive heart failure (NYHA class III or IV)
- New permanent pacemaker implantation resulting from new or worsened conduction disturbances
- New onset of atrial fibrillation or atrial flutter
- Coronary obstruction: periprocedural ( $\leq 72$  hours post index procedure)
- Ventricular septal perforation: periprocedural ( $\leq 72$  hours post index procedure)
- Mitral apparatus damage: periprocedural ( $\leq 72$  hours post index procedure)
- Cardiac tamponade: periprocedural ( $\leq 72$  hours post index procedure)
- Prosthetic aortic valve malpositioning, including valve migration, valve embolization, or ectopic valve deployment
- TAV-in-TAV deployment
- Prosthetic aortic valve thrombosis
- Prosthetic aortic valve endocarditis

Details on the CEC events and procedures are outlined in the CEC charter. Tests and images required to adjudicate these events are specified in the event definitions (see Table 26.2-1).

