### **10.1.4. U.S. Continued Access Study Subjects**

For the U.S. Continued Access Study cohort, subjects confirmed eligible for the study by the CRC (see Section 22.2) and who provided written informed consent are considered enrolled in the study as soon as an attempt is made to insert the Lotus Valve System into the subject's femoral artery.

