**Table 11.1-1: Study Event Schedule**

Assessment	Screening a	Baseline	Procedure	Within 1 Day Post-procedure	Prior to Discharge or 7 Days Post-Procedure	30 Days b (±7 Days) Office Visit	6 Months b (±30 Days) Office Visit	12 Months b (±30 Days) Office Visit	24–60 Months b [Annual] (±45 Days) Office Visit
------------	------------------------	----------	-----------	-----------------------------	---	---	---	--	--

Imaging Core Laboratory procedure guidelines (see study Manual of Operations). Results must be forwarded to the CT/X-Ray Core Laboratory for analysis. If additional imaging is performed (e.g., cardiac CT or MRI scan), data may be provided for analysis.

- o: Includes the Kansas City Cardiomyopathy and SF-12 QOL questionnaires. Baseline QOLs should be performed within 30 days prior to the index procedure.
- p: QOL survey at 36 and 60 months.
- q: Procedural cine-angiogram including final post-deployment aortogram of the ascending aorta must be done and sent to the CT/X-Ray Core Laboratory for analysis.
- r: For subjects who received a permanent pacemaker related to the index procedure, pacemaker dependence must be captured at the 30-day and 1-year visits via pacemaker interrogation. Pacemaker interrogation should also include assessment of the percentage of beats where the ventricles are paced.
- s: AEs and ADEs will be monitored and collected from the time of enrollment through 12-month follow-up. For subjects who do not receive the study device, AEs will be monitored through 1-year follow-up.
- t: Information on device deficiencies for the test and the control devices, as well as all SAEs, SADEs, UADEs, USADEs, and CEC events will be monitored and reported to Boston Scientific for all enrolled subjects from the time of enrollment through termination of the study. For subjects who do not receive a study device (test or control), the mentioned events will be monitored through 1 year post-index procedure. Please refer to Section 7.2 for a list of CEC events and Table 26.2-1 for definitions of these events, which specify data required for CEC adjudication. Complaint reporting of any device deficiencies for any commercially available products used should also be carried out using the manufacturer’s processes.

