##### 11.7.2.1. Valvuloplasty

A balloon valvuloplasty on the native valve following standard techniques must be performed with an appropriately sized valvuloplasty balloon (avoid oversizing). Careful attention should be paid to the position of the guidewire throughout the procedure. Prior to introduction of the Lotus Valve System or LOTUS Edge Valve System, the subject's hemodynamic status and heart rhythm must be assessed, and a heart rhythm strip should be obtained (12-lead ECG is not required).

Information on the balloon valvuloplasty, including number of inflations, should be documented in the source data and will be captured in the eCRFs.

**Note:** If the subject becomes hemodynamically unstable after the valvuloplasty for reasons unrelated to the aortic valve annulus and/or leaflets, the Lotus Valve implantation (using the Lotus Valve System or the LOTUS Edge Valve System) should be interrupted until the subject is stable.

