### **12.2.4. Reporting Events**

For all subjects in the roll-in (with the 23 mm, 25 mm, or 27 mm Lotus Valve), Lotus 21 mm Nested Registry, LOTUS Edge Nested Registry, roll-in with the 29 mm LOTUS Edge Valve, LOTUS Edge 29 mm Nested Registry, and U.S. Continued Access Study cohorts, all events that occur from the start of the index procedure will be reported. For all randomized subjects, events from the time of randomization onward will be reported. For randomized subjects who do not have an attempted procedure, events from the date of randomization to 1 year post-randomization will be reported. For time based clinical events, the cut-off for events for 30-day endpoints will be 30 days, for 6-month endpoints will be 180 days, for 1-year endpoints will be 365 days, and for 2-5 year endpoints will be 365 days times the number of years. For events at discharge or 7 days post-procedure, the cut-off for events will be the earlier of the date of discharge or 7 days post-procedure for each subject.

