**Table 21.3-1: Investigator Reporting Requirements**

Event Classification	Communication Method	Communication Timeline
Unanticipated Adverse Device Effect / Unanticipated Serious Adverse Device Effect (UADE/USADE)	Complete adverse event (AE) electronic case report form (eCRF) page with all available new and updated information	
 
Within 1 business day of first becoming aware of the event
 
Beginning from time of enrollment for all subjects
 
Terminating at the end of the study
 

	Provide copies of all relevant source documents requested by BSC	
 
As soon as possible after reporting the event
 

Serious Adverse Event (SAE) including Serious Adverse Device Effects (SADE)	Complete AE eCRF page with all available new and updated information	
 
Within 2 business days of first becoming aware of the event or as per local/regional regulations.
 
Beginning from time of enrollment for all subjects
 
Reporting required through the end of the study
 

	Provide all relevant source documentation (unidentified) for reported event	
 
When documentation is available
 

Adverse Event (AE)	Complete AE eCRF page	
 
As soon as possible before the next planned monitoring visit
 
Beginning from time of enrollment
 

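### In the six non-randomized cohorts, required event collection starts at attempted valve insertion, but Section 12.2.4 reports events from the start of the procedure, so complications of access and valvuloplasty need not be recorded

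*Combined protocol and SAP*

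**What the plan says.** Two rules govern when events begin to count in the six non-randomized cohorts: the initial roll-in, the Lotus 21 mm registry, the U.S. Continued Access cohort, the LOTUS Edge registry, the 29 mm roll-in and the 29 mm registry.

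**Collection.** Section 21.1 states that "event reporting (eCRF) is required beginning from the time an attempt is made to insert" the Lotus or LOTUS Edge system into the femoral artery. Sections 10.1.1 and 10.1.3 to 10.1.6 make that attempt the point of enrollment. In the Continued Access wording, subjects "are considered enrolled in the study as soon as an attempt is made to insert the Lotus Valve System into" the femoral artery. Other collection rules are tied to enrollment:

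- Table 11.1-1, footnote s: "AEs and ADEs will be monitored and collected from the time of enrollment through 12-month follow-up".
- Table 11.1-1, footnote t, for serious events and events for adjudication by the Clinical Events Committee (CEC): "for all enrolled subjects from the time of enrollment through termination of the study".
- Table 21.3-1, for unanticipated device effects, serious events and adverse events: "Beginning from time of enrollment for all subjects".

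**Reporting.** For the same six cohorts, Section 12.2.4 says that "all events that occur from the start of the index procedure will be reported".

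The randomized cohort has an earlier start: "For the randomized cohort, event reporting (eCRF) is required beginning from the time of randomization".

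**The concern.** The start of the procedure and the attempt to insert the valve system are different moments, and invasive work is done between them. If a site follows Section 21.1 to the letter, a complication of arterial access or valvuloplasty that begins before the valve catheter is introduced does not have to be entered. Section 12.2.4 nevertheless says it will be reported. The protocol gives no order of precedence between the two sections.

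At stake is how completely procedural safety is ascertained in cohorts meant to describe it. Bleeding, major vascular complications, stroke and tamponade are all CEC-adjudicated, and all can arise early in the procedure. If some sites record them from first puncture and others only from valve insertion, the descriptive rates mix two collection windows. They also rest on a shorter required window than the randomized Lotus arm, where reporting begins at randomization.

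**Working it through.** The plan states no figure for this point, so the check sets the start rules beside the order of the procedure and then counts the subjects concerned.

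**1. Order of the procedure (Section 11.7.2)**

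| Step | Source | Inside the Section 12.2.4 window? | Inside the required collection window? |
|---|---|---|---|
| Femoral puncture and introducer placement | 11.7.2; puncture and introducer times listed in 11.7.2.2 | Yes | No |
| Balloon valvuloplasty | 11.7.2.1: "A balloon valvuloplasty on the native valve following standard techniques must be performed" | Yes | No |
| Valve catheter inserted through the introducer | 11.7.2.2, step 2 | Yes | Yes, from here |
| Valve release, introducer removal, closure | 11.7.2.2, steps 6 to 10 | Yes | Yes |

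The first two rows are the gap.

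**2. Could introducer placement count as inserting the valve system?** No. Sections 5.1.3 and 8.2.1 treat the Lotus Introducer Set as an accessory, separate from the valve system. Table 21.3-1 also keeps the two moments apart: device deficiencies are reportable from introducer sheath insertion, while adverse events wait for enrollment. The safety section therefore has its own second start point, and Section 12.2.4 adds a third.

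**3. Can reportable complications arise in the gap?** The protocol expects that they can. Section 19.1 counts catheterization and valvuloplasty among the sources of procedural risk. The note in Section 11.7.2.1 deals with instability after valvuloplasty. Table 26.2-1 includes access-related vascular injury among major vascular complications when it has serious consequences.

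**4. Planned subjects under the later start (Section 8.3)**

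- Initial roll-in 120, 21 mm registry 20, Continued Access 1000, LOTUS Edge registry 50, 29 mm roll-in 20, 29 mm registry 20.
- 120 + 20 + 1000 + 50 + 20 + 20 = 1230.
- Check: 1230 + 912 randomized = 2142, the stated total.
- Share: 1230 / 2142 = 57.4%.

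The 50 is a minimum and the other five counts are maxima, so 1230 is approximate.

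**5. Planned subjects in the non-randomized cohorts with a regulatory analysis (Section 12.3.2)**

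- 21 mm registry 20, LOTUS Edge registry 50, 29 mm cohorts 20 + 20 = 40.
- 20 + 50 + 40 = 110, and 110 / 1230 = 8.9%.

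The 29 mm analysis uses only the first 30 implanted subjects, pooled with a European study, so it would draw on at most 30 of those 40. No regulatory analysis is listed for the Continued Access or initial roll-in subjects (1000 + 120 = 1120).

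**6. Number of events affected.** This cannot be computed. The documents do not give the share of procedural events with onset before valve insertion.

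**The case against.** The strongest reply is that the data may be captured anyway. Section 21.1 says when reporting becomes mandatory and does not forbid earlier entries. Section 11.7.2.2 lists adverse event assessment among the data gathered during the procedure, beside puncture, introducer and valvuloplasty details. Table 11.1-1 marks event assessments in the Procedure column, and Section 12.2.4 is itself protocol text. A reader might infer that pre-insertion events will be missing from the database. The documents do not support that; they support only that capture is not guaranteed. The reply does not close the gap, because neither the procedure list nor the schedule column sets a start time, while Section 21.1, the footnotes and Table 21.3-1 do.

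The exposed set is also narrow. Only events with onset before the insertion attempt are affected. Complications at introducer removal or closure are inside the window. Table 26.2-1 defines a neurological event as a deficit appearing after the subject emerges from anesthesia, so where anesthesia is used a procedural stroke would normally be recognized after insertion. This stands as a limit on size.

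Finally, Section 12.1 summarizes these cohorts separately and without inference, and no comparison with the randomized Lotus arm is planned. A reader might infer that rates will look better than in that arm, or that regulatory conclusions about all 1230 subjects are compromised. Neither follows: the direction is possible but its size is unknown, and the listed regulatory analyses concern cohorts with about 110 planned subjects.

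**Conclusion.** The point holds as an internal contradiction with a practical consequence. The required collection window opens later than the window Section 12.2.4 promises to report, and the interval contains arterial access and a mandatory valvuloplasty. Procedural event rates in the non-randomized cohorts could be understated, and sites could differ in what they enter.

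The scope is about 1230 planned subjects; that is a count of people under the rule, not of lost events. The conclusion assumes that sites treat the explicit start rules as binding and that the order of steps in Section 11.7.2 is followed. The powered safety, effectiveness and regurgitation endpoints use only the randomized cohort and are not touched. This is a low-severity correction, worth making because it is cheap and concerns safety ascertainment.

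**What to change.** For every subject in the six cohorts who becomes enrolled, start event reporting at the start of the index procedure, defined as first vascular puncture. Make the change in Section 21.1, in the adverse event, serious event and unanticipated device effect rows of Table 21.3-1, and in footnotes s and t of Table 11.1-1. Changing only the first two would leave the contradiction in the footnotes. Because the table and footnotes cover all subjects, the new wording should be specific to these cohorts, leaving the randomized cohort's start at randomization as it is. Section 12.2.4 then needs no change.

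The cost is protocol wording, one eCRF instruction and a few more events to record. Puncture time is already collected under Section 11.7.2.2.

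One group is left out. A subject whose procedure ends at access or valvuloplasty is never enrolled in these cohorts, so appears in neither the event counts nor the denominators. This change does not address them.
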